The study will be a single center, double-blinded, placebo-controlled randomized clinical trial conducted at Washington University School of Medicine.

E2 Subject Selection

2.a Inclusion Criteria

- 1) Adults age 18 to 70
- 2) Diagnosis of COVID at least 6 months prior to study enrollment with self-reported parosmia
- 3) Ability to read, write, and understand English
- 4) Score of at least 40 on DiSODOR during screening and at least 25 during Visit 1

2.a Exclusion Criteria

- 1) History of smell loss or change prior to COVID-19 infection
- 2) History of conditions known to impact olfactory function:
 - a. Chronic rhinosinusitis
 - i. If individual notes a history of chronic rhinosinusitis or prior endoscopic sinus surgery, they may be eligible if they can a note from their otolaryngology (ENT) physician stating the following:
 1. Patient's chronic rhinosinusitis is controlled
 2. There are no polyps/masses/scarring of the olfactory cleft
 3. The otolaryngologist feels that the patient's parosmia is secondary to COVID-19
 - b. History of prior sinonasal or skull base surgery
 - c. Neurodegenerative disorders (Parkinson's disease, Huntington's disease, Amyotrophic lateral sclerosis, Lewy body dementia, frontotemporal dementia)
- 3) Currently using concomitant therapies specifically for the treatment of olfactory dysfunction
- 4) Inability to tolerate a needle injection into the neck
- 5) History of coexisting conditions that make SGB contraindicated:
 - a. Unilateral vocal cord paralysis
 - b. Severe COPD (FEV1 between 30-50% of predicted)
 - c. Recent myocardial infarction within the last year

- d. Glaucoma
- e. Cardiac conduction block of any degree
- 6) Currently taking blood thinners or antiplatelet agents, including
> 81mg aspirin
- 7) Allergy to local anesthetic
- 8) Inability to extend the neck for any reason (e.g., severe arthritis)
- 9) History of prior stellate ganglion block

2.b Ethical Considerations

Patients will be informed in the informed consent process that they may or may not personally benefit from the study and that the data obtained from the study will be used to inform the future care patients with chronic COVID-19-induced olfactory dysfunction. There will be phone assistance available 24/7 during the study period to report any possible adverse reactions. There are no financial conflicts of interest.

2.c Subject Recruitment Plans and Consent Process

Study recruitment strategies include:

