Blinding. Blinding will be achieved through two primary means. First, the Barnes Jewish Hospital investigational drug pharmacy will produce identical appearing mepivacaine and saline vials of which the entire research team will be unaware of the participant's intervention assignment. Second, a single-use eye patch will be placed prior to the procedure. Additionally, a cool compress will be applied to each participant's ipsilateral eye prior to the procedure and kept in place throughout the procedure and during the post-procedure recovery for a total of up to 20 min of cool compress application. Once subjects have been approved for discharge from the CTRU, participants will be asked to wear the single-use eye patch for an additional 2 hours prior to patch removal. All subjects will be informed that Horner's syndrome can occur regardless of injection of mepivacaine or placebo.

2.e Risks and Benefits

Risks of lidocaine/mepivacaine injection (SGB) include:

- allergic reactions like skin rash, itching or hives, swelling of the face, lips, or tongue
- breathing problems
- changes in vision
- chest pain
- feeling faint or lightheaded, falls
- headache
- seizures
- slow, irregular heartbeat
- trembling or shaking
- unusually weak or tired
- confusion
- ringing in your ears

If a participant experiences any side effect listed above following the injection, the post-injection observation period will last up to 2 hours. Vital signs (heart rate and breathing) will be monitored throughout the observation period.

Side effects that are expected, common, usually lasting up to 24 hours and usually do not require medical attention:

- Horner syndrome - constricted pupil (miosis), drooping of the upper eyelid (ptosis), absence of sweating of the face (anhidrosis), and sinking of the eyeball into the bony cavity that protects the eye (enophthalmos).
- anxiety or nervousness
- backache
- feelings of cold, heat, or numb
- irritation at site where injected
- nausea, vomiting
- hoarseness
- mild shortness of breath
- dysphagia (difficulty swallowing)
- globus (feeling of something stuck in the throat)

- congestion- nasal
- temporary weakness in the arm
- blurry vision
- droopy eye lid
- eye redness
- neck pain or pain at injection site

However, these side effects are all rare when used at the maximum total combined dose of 4.5mg/kg lidocaine and 4.5mg/kg mepivacaine. We will strictly follow this dosing guideline.

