Participants may or may not directly benefit from the stellate ganglion blocks and will be aware that they may receive the saline injection (without active medication). Regardless of the results, our findings will help direct future care of patients with a similar condition.

2.f Early Withdrawal of Subjects

During the informed consent process, participants will be informed that they may withdraw at anypoint during the study, including before, during, or after their SGB. Participants will face no penalty or negative consequences for withdrawaling from the study.

E3 Study Drug

3.a Treatment Regimen

Stellate Ganglion Block. All SGBs will be performed by a board-certified anesthesiologist and pain management specialist with extensive experience performing SGBs ([name]). Laterality of the SGB will be randomized between the left and right sides of the neck. Participants will be asked to remain NPO for 8 hours prior to the SGB. Using ultrasound-guidance, the transverse process of the C6 vertebra is identified. Color-doppler is used to identify blood vessels. A 27-gauge needle is used to anesthetize the superficial skin with 1% lidocaine. Then, a 21-gauge ultrasound needle is advanced using an in-plane technique from lateral to medial with careful avoidance of neurovascular structures. After negative aspiration, 6-8 mL of 1% mepivacaine is deposited beneath the prevertebral fascia and above the longus colli muscle into the stellate ganglion.

The presence of a transient Horner syndrome (ipsilateral miosis, anhidrosis, and ptosis) 5-15 minutes after the SGB is expected. Post-procedure adverse effects will be documented. If participants develop globus or dysphagia they are asked to remain NPO for an additional 2 hours post-procedure.

All participants will be monitored for adverse effects prior to, during, and immediately following each SGB. A continuous electrocardiogram (ECG) is run from just prior to the start of the procedure until ten minutes following its completion. Vital signs, including pulse oximetry, blood pressure, heart rate, and respiratory rate will be obtained prior to the beginning of the procedure and repeated until ten minutes post-procedure.

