Placebo Injection. The placebo sham injection will be performed in an identical fashion as the stellate ganglion block by [name] with the exception of using 6-8 mL of 0.9% saline injection instead of mepivacaine. A Horner syndrome is not expected after placebo injection, but its presence has been noted in prior studies with sham SGBs.

F Study Procedures

F1 Screening for Eligibility

To determine potential eligibility for the study, the research team will query the medical record and our team's contact database of COVID-19-induced olfactory dysfunction patients based on the inclusion/exclusion criteria. For those meeting the selection criteria, we will access name, telephone number, age, sex, and date/time of any upcoming clinic visits. For interested and potentially eligible individuals, including those contacting the study team, eligibility will be determined based on the inclusion/exclusion criteria and completion of the DisODOR questionnaire. If they have been treated at the medical center for COVID, their medical record will be accessed.

F2 Schedule of Measurements

The first visit will be completed at the Clinical and Translational Research Unit (CTRU). The second and third visits will be completed virtually.

Role of the CTRU: Nursing staff will be needed for assistance in completion of the SGB. Additionally, all subjects will have vital signs monitored with serial blood pressures, respiratory rate, heart rate, and pulse oximetry within the CTRU for a minimum of 10 minutes after completion of the block to ensure patient stability prior to discharge. Additional monitoring will be provided as needed based on patient response to the procedure. Participants will be discharged once stability is determined and instructed to continue wearing an eye patch for an additional 2 hours. It will be ensured that they have someone to drive them home prior to discharge.

Visit 1

At the initial visit, demographic information, including age, sex, race, and length of time of parosmia will be collected from each enrolled patient. Prior to undergoing the first SGB, participants will complete the Parosmia trigger question, DisODOR, UPSIT, CGI-S for Parosmia, OCS, HADS, and Pre-Intervention Expectations Questionnaire. The assessment of the blind will occur just prior to discharge from the first visit.

Visit 2

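### The COPD exclusion is a band (FEV1 30-50% of predicted), so as written it does not exclude a candidate with FEV1 below 30%

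*Combined protocol and SAP*

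**What the plan says.** Section E2, exclusion criterion 5, is headed "History of coexisting conditions that make SGB contraindicated" and lists five items, a to e. Item b is "Severe COPD (FEV1 between 30-50% of predicted". The other four concern vocal cord paralysis, recent myocardial infarction, glaucoma and cardiac conduction block. COPD and FEV1 appear nowhere else in the document.

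Section F1 states how candidates are judged: "eligibility will be determined based on the inclusion/exclusion criteria and completion of the DisODOR questionnaire". The schedule of events in section F2 lists no spirometry.

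On safety, section 2.e names "breathing problems" among the risks of the injection and says that, if a listed side effect occurs, "the post-injection observation period will last up to 2 hours". Section E3, 3.a says "All SGBs will be performed by a board-certified anesthesiologist and pain management specialist" and "Vital signs, including pulse oximetry, blood pressure, heart rate, and respiratory rate will be obtained prior to the beginning of the procedure", with vital signs repeated until ten minutes afterwards.

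**The concern.** An exclusion meant to protect people with poor lung function should become stricter, or at least stay in force, as lung function worsens. This one stops applying below 30% of predicted. The people it leaves out are those with the least respiratory reserve.

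The protocol itself treats the item as a contraindication, so it is a participant-safety limit. Respiratory effects of the block are also an observed feature. The pilot table in section D2 gives mild shortness of breath in 7 of 40 procedures (7/40 = 17.5%), and section 2.e lists it among the expected side effects. Allocation is 2:1 to active treatment (section 2.d), so a candidate admitted through the gap has a two-in-three chance of receiving the mepivacaine block.

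**Working it through.** The plan gives no calculated figure here, so the check is a reading of the rule at specific values, followed by a search for anything else that would exclude the same candidates.

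**Step 1. The rule as an interval.** Taking both ends as inclusive, 5b excludes a candidate with COPD if 30 ≤ FEV1 (% of predicted) ≤ 50. A one-sided rule excludes if FEV1 ≤ 50.

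| FEV1, % of predicted | 5b as written | One-sided rule |
|---|---|---|
| 60 | not excluded | not excluded |
| 50 | excluded | excluded |
| 45 | excluded | excluded |
| 30 | excluded | excluded |
| 29 | not excluded | excluded |
| 25 | not excluded | excluded |

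The two rules differ only below 30. Nobody who is now excluded would become eligible.

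**Step 2. Does another criterion close the gap?**

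- Exclusions 1 to 3 concern earlier smell loss, conditions that affect olfaction, and concurrent treatment.
- Exclusion 4 concerns tolerating a needle in the neck, and exclusion 8 concerns extending the neck.
- Items 5a and 5c to 5e are the vocal cord, cardiac and eye conditions.
- Exclusions 6, 7 and 9 concern anticoagulant or antiplatelet drugs, anesthetic allergy and a previous block.
- The inclusion criteria cover age, COVID history with parosmia, English and the DisODOR score.

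None refers to lung function. Criterion 5 has no wording that makes its list illustrative, and no exclusion at the investigator's discretion is written.

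**Step 3. Does the history wording close it?** Partly. A person now below 30% whose FEV1 was previously in the band has a history of the listed condition. A person with no such earlier value is not covered on a literal reading.

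**Step 4. Does a later step close it?** Oximetry and other vital signs are taken before the block, but the document gives no oximetry or lung-function value at which the block is withheld. The ten-minute monitoring and the extended observation apply after the injection. Criterion 5b is therefore the only stated lung-function limit.

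**The case against.** The strongest reply is that nobody would read the item this way. It is labelled severe COPD and sits under contraindications, so a worse grade is contraindicated all the more. Item 5a is drafted similarly: it names unilateral vocal cord paralysis and says nothing of bilateral, yet it can hardly be meant to admit bilateral cases. On this view the list names threshold conditions, and the bracket is only a gloss. The trial also measures no FEV1, so in practice the item turns on a known diagnosis and grade. An experienced anesthesiologist sees oximetry before the needle goes in. The pilot reported no serious adverse events, and all its adverse events were transient.

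Much of this stands. The intent is clear, the pre-procedure check is a real safeguard before exposure, and the practical risk is likely small. The risk list in section 2.e is general and does not mention COPD. The pilot does not report participants' lung function, so it settles nothing about people below 30%.

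What does not stand is that intent repairs the text. Item 5a gives no numerical limits, whereas 5b defines its condition by a range with an explicit floor. Section 2.c has a research team member approach candidates for screening, and F1 ties eligibility to the criteria as written. The anesthesiologist may well decline such a patient, but no stated value requires it.

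**Conclusion.** The concern holds. Read as written, criterion 5b excludes FEV1 from 30% to 50% of predicted and leaves the whole range below 30% outside the exclusion. This is a drafting gap in a safety criterion, and confidence in that reading is high.

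The consequence cannot be measured from the documents, which give no number of candidates with COPD or with FEV1 below 30%. I assume few, possibly none, among up to 140 participants. No sample size, power, error rate or analysis figure depends on it. The amendment should be made because the item is a stated contraindication, a literal application gives the wrong result, and the correction costs almost nothing.

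The conclusion assumes that the band is inclusive at both ends. If it were exclusive, exactly 30% and exactly 50% would also fall outside it, and the gap below 30% would be unchanged.

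**What to change.** Remove the lower bound in exclusion criterion 5b. Suggested wording: severe or very severe COPD (FEV1 at or below 50% of predicted). Naming both grades also helps a screener who has a recorded diagnosis but no FEV1 value. The sponsor's clinicians should confirm that 50% is the limit they want.

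The cost is one phrase in an amendment. The effect on recruitment should be negligible, since the only people newly excluded are those with COPD and FEV1 below 30%. No statistical section needs to change.

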The second visit will be virtual and will occur approximately 1 month after the first visit. Participants must have access to email and the internet to receive a link which will

connect them with the questionnaires to complete about their smell ability and how they are feeling. Their answers will be saved in REDCap. Participants will be asked to fill out the Parosmia trigger question and the DisODOR. They will also complete the CGI-I for Olfactory Dysfunction, the LCQ, the Participants Satisfaction with Treatment Questionnaire, OCS, HADS, and Adverse Events Assessment.

Visit 3

The third and final visit will be virtual and will occur approximately 3 months after the injection. Participants must have access to email and the internet to receive a link which will connect them with the questionnaires to complete about their smell ability and how they are feeling. Their answers will be saved in REDCap. At 3-months post-SGB, participants will virtually complete the Parosmia trigger question, DisODOR, CGI-I for Olfactory Dysfunction, LCQ, Participant Satisfaction with Treatment Questionnaire, OCS, HADS, and Adverse Events Questionnaire.

Schedule of Events	Visit 1		Visit 2 1 Month post SGB (=+/- 7 days)	Visit 3 3 Months post SGB (+/- 7 days)
	Screening*	Baseline		
Informed Consent	X			
Demographics Questionnaire**	X			
Inclusion/Exclusion Criteria	X			
Parosmia trigger question		X	X	X
CGI-S for Parosmia		X		
University of Pennsylvania Smell Identification Test (UPSIT)		X		
Pre-Intervention Expectations Questionnaire		X		
Parosmia Olfactory Dysfunction Outcomes Rating (DisODOR)	X	X	X	X
Olfaction Catastrophizing Scale (OCS)		X	X	X
Hospital Anxiety and Depression Scale (HADS)		X	X	X
Long-COVID Questionnaire		X	X	X
SGB or Placebo Injection		X		

Assessment of the Blind		X		
CGI-I for Parosmia			X	X
Participant Satisfaction with Treatment Questionnaire			X	X
Adverse Events Assessment		X	X	X

*Screening and Visit 1 may occur at the same visit

**Demographic variables include date of birth, sex, race, ethnicity, home address, date of (+) COVID-19 test

***The assessment of the blind will occur just prior to discharge from the first visit.

F3 Safety and Adverse Events

3.a Safety and Compliance Monitoring

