The specific monitoring plan for this study is based on the potential risk of participation and size and complexity of the planned investigation. Based on these considerations, this study will have a monitoring board comprised of [name], [name], [name], [name], and [name], the study biostatistician. The monitoring board will meet to review data after enrollment of 20 participants. All reports of a Serious Adverse Event (SAE) or an Unexpected Adverse Event will be investigated by the monitoring team and reported to Washington University HRPO according to the reporting requirements.

3.b Adverse Events

Adverse events will be tracked from the time of dose administration through post dose and at the follow up visit 3 for drug-related adverse events. All adverse events will be documented and assessed for relatedness to the study medication. The study team will monitor for adverse events on an ongoing basis. Once the team becomes aware of an adverse event, the AE will be reported according to institutional guidelines.

G Statistical Plan

G1 Sample Size Determination and Power

Sample size estimate for the proposed study is based on our team's previous pilot study with 50% of participants reporting slightly improved olfactory dysfunction at 1 month.

A power analysis was performed using Fisher's exact test in G-Power 3.1.2. Our recently completed SGB trial showed that 1 month after injection, 35% of the participants had an improvement of 15 points or more in ODOR total score. Using a clinically important difference of 25% in proportions of responders between active treatment and control group, we estimated using an exact test that a sample size of 114 subjects (38 controls

and 76 cases) will be needed to detect with 80% power at the 2-sided alpha level of 0.05.

Considering a 20% drop-out rate the total sample size to enroll is up to 140 participants.

G2 Interim Monitoring and Early Stopping

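### The adverse-event rule in F3 3.b conflicts with the visit schedule and attributes harm to the drug alone, and effects that emerge after discharge may be under-recorded

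*Combined protocol and SAP*

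**What the plan says.** **Collection times.** F3 3.b states: "Adverse events will be tracked from the time of dose administration through post dose and at the follow up visit 3 for drug-related adverse events". Visit 2 is not named. In F2, the Visit 2 text lists "OCS, HADS, and Adverse Events Assessment" among the forms, the Visit 3 text lists an adverse-events questionnaire, and the schedule table marks the assessment on the injection day, at Visit 2 and at Visit 3. None of these is limited to drug-related events. On Visit 2 timing, F2 says: "The second visit will be virtual and will occur approximately 1 month after the first visit"; the table gives a window of 7 days either side.

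**Relatedness.** F3 3.b continues: "All adverse events will be documented and assessed for relatedness to the study medication". E3 3.a describes the placebo as the same injection with saline in place of mepivacaine.

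**The eye on the injection day.** Under Blinding in E2 2.d, "a single-use eye patch will be placed prior to the procedure". A cool compress on the same-side eye is "kept in place throughout the procedure and during the post-procedure recovery for a total of up to 20 min". The patch is worn for 2 more hours after discharge. E3 3.a says: "The presence of a transient Horner syndrome (ipsilateral miosis, anhidrosis, and ptosis) 5-15 minutes after the SGB is expected". F2 sets at least 10 minutes of monitoring after the block.

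**Duration.** E2 2.e heads its list of common effects, Horner syndrome among them, with "Side effects that are expected, common, usually lasting up to 24 hours". D2 says Horner syndrome improves over a few hours.

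**The concern.** Three separate weaknesses bear on secondary aim 2.

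1. The two statements of when adverse events are collected cannot both be followed. A team working from F3 3.b alone would not ask at Visit 2, and at Visit 3 would record only events already judged drug-related.
2. The exposure under study is a needle procedure plus a drug, and the procedure is common to both arms. A relatedness judgement confined to the drug has no place for harm from the needle. In the saline arm it has little meaning at all.
3. The commonest pilot effect has its main signs in an eye that is covered when they are expected. The cover comes off at home, and no adverse-event contact is scheduled for about a month.

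At stake are the event rates reported for the block, the block-minus-saline difference in those rates, and the count of events attributable to the intervention. A transient event not recorded near the time can later be obtained only from memory.

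**Working it through.** **Check 1: the two collection rules side by side.**

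| Time | F3 3.b | F2 visit text and table |
|---|---|---|
| Injection day | Tracked from dosing through post dose | Assessment marked |
| Visit 2 (about 1 month) | Not named | Assessment required |
| Visit 3 (about 3 months) | Drug-related events | Assessment required, no limit |

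They differ at Visit 2 on whether to ask, and at Visit 3 on what to keep. The next sentence of F3 3.b says all events are documented, which sits uneasily with the drug-related limit just before it.

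**Check 2: the timeline for an effect that is short or covered.** Minutes run from the end of the block; a month is taken as 30 days.

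- Horner onset: 5 to 15 minutes (E3 3.a).
- Earliest discharge: 10 minutes (F2), so at the minimum stay the last 15 − 10 = 5 minutes of the onset window fall after discharge.
- Patch removal: at least 10 + 120 = 130 minutes. The whole onset window lies under the cover.
- Usual duration of common effects: up to 24 hours, that is, to about day 1.
- Visit 2: 30 − 7 = day 23 to 30 + 7 = day 37.
- Visit 3, the first follow-up if F3 3.b is read literally: 90 − 7 = day 83 to 90 + 7 = day 97.

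An effect first noticed after discharge and gone within a day is therefore solicited for the first time at least three weeks later. No section says who inspects the lid or pupil under the patch, or how that would be done without unblinding staff. The J1 list of questionnaires includes no adverse-event form, so the wording of the Visit 2 question cannot be judged.

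**Check 3: the scale of the effect most exposed to this.** The pilot table in D2 gives Horner syndrome in 39 of 40 procedures; 39/40 = 97.5%, as printed. Under 2:1 allocation, active participants number 114 × 2/3 = 76 at the required sample size, or 140 × 2/3 ≈ 93 at the enrolment ceiling. At the pilot rate that is 0.975 × 76 ≈ 74 to 0.975 × 93 ≈ 91 expected cases.

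The documents give no probability *c* that a case is recorded. Treating *c* as an assumption, recorded rate = *c* × 97.5%:

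| Assumed *c* | Recorded rate |
|---|---|
| 25% | 24% |
| 50% | 49% |
| 75% | 73% |
| 100% | 97.5% |

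If *c* were the same in both arms, the block-minus-saline difference would shrink by the same factor. This shows only how the result depends on *c*; it does not estimate the loss.

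**Check 4: attribution.** Take an injection-site bruise in a saline participant. F3 3.b would have it documented and then judged against the study medication, which here is saline. There is no field in which to call it related to the injection, so a tally of related events could omit it even though the full listing holds it.

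**The case against.** The strongest reply is that much of the safety record does not depend on the weak points.

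- E3 3.a has participants monitored before, during and straight after the injection, with post-procedure effects documented, and F2 schedules an assessment that day. Hoarseness (17 of 40 pilot procedures) and globus (14 of 40) are not hidden by a patch. A reader might infer that injection-day effects in general will be lost; the documents do not support that.
- Ten minutes is a minimum. F2 allows longer monitoring, and E2 2.e extends observation to as much as 2 hours if an effect on its first list occurs, which includes vision changes. Horner syndrome is on the second list, so it does not itself trigger the extension.
- E2 2.b provides a phone line at all hours, and F3 3.b promises ongoing monitoring. It would be wrong to say that nothing is collected for a month. What is absent is scheduled, solicited collection, and effects described as usually needing no medical attention are unlikely to prompt a call.
- A reader might infer that needle harms will go missing or be filed as unrelated. F3 3.b says all events are documented, E2 2.e lists injection-site pain as expected, and the pilot table counted site pain and bruising as at least possibly related to the study. An arm-by-arm comparison of all events does not use the relatedness label. The gap is in attribution, plus the Visit 3 limit.
- The eye cover is a deliberate blinding measure. Asking about lids and pupils the next day would direct participants to the sign that best separates the arms, in a trial whose primary outcome, DisODOR, is self-reported and whose blind is assessed only before discharge at Visit 1. This objection stands, and it shapes the fix.

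What survives is the conflict between sections, the drug-only attribution, and the absence of a scheduled question while post-discharge effects last.

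**Conclusion.** The point holds in three parts of differing strength.

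- **Certain from the text:** F3 3.b conflicts with F2 on Visit 2 and on the scope of Visit 3. The passages must be reconciled.
- **Certain from the text, with a limited consequence:** relatedness is judged to the drug only, so harm from the injection can be recorded but not attributed to the study intervention in either arm.
- **Plausible, size unknown:** Horner eye signs and other effects that emerge after discharge may be under-recorded, because the next scheduled question falls at about day 23 to 37 against a usual duration of up to 24 hours. This assumes that staff do not look under the patch, that recall at Visit 2 is incomplete, and that phone reporting is partial. The documents neither confirm nor exclude these.

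A stronger reading, that the block's event rates and the difference from saline will come out too low, is tempting but not established: no capture rate is given. The primary efficacy analysis is not affected by this point.

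**What to change.** 1. Reword F3 3.b so that all adverse events, whatever their presumed cause, are collected at Visits 1, 2 and 3, matching the F2 table.
2. Replace the single relatedness judgement with two fields, study drug and injection procedure, completed in both arms by staff who remain blinded.
3. Send one general REDCap adverse-event checklist to both arms the day after injection, with onset, duration and an open item for any other effect. Leave out specific eyelid or pupil prompts.
4. Repeat the existing blind-assessment question at Visit 2, after DisODOR is completed, so that any unblinding can be measured. Read it beside the Visit 1 answer, since a guess at one month may also reflect perceived benefit.

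Items 1 and 2 need only a wording change and one extra form field. Item 3 costs one short emailed form; participants already need email and receive REDCap links for Visits 2 and 3. Its drawback is a small unblinding risk, limited by the general wording and by the existing statement to participants that Horner syndrome can occur in either arm. Omitting eye prompts means that mild eye signs may still be missed, which is the price of protecting a self-reported primary outcome. No dose, procedure, observation period or clinical rule changes.
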